PROTOCOL

SAFETY STUDY IN RETINAL TRANSPLANTATION FOR DRY AGE RELATED MACULAR DEGENERATION

PRINCIPAL INVESTIGATOR: [name]., Clinical Professor,
Dept. Ophthalmology & Visual Sciences,
Univ. of Louisville School of Medicine;
Retina Vitreous Resource Center
Norton Audubon Hospital, Louisville

PROTOCOL NO.: WIRB[®] Protocol #20050380

CO-INVESTIGATORS: [name]., Assistant Professor;
Depts. Ophthalmology and Cell & Neurobiology,
Doheny Retina Institute
Univ. of Southern California, Los Angeles

[name]., Adjunct Professor
Dept. Anatomical Sciences & Neurobiology
University of Louisville School of Medicine

[name]., Professor;
Dept. Ophthalmology & Visual Sciences,
Dept. Psychological and Brain Sciences
Univ. of Louisville School of Medicine

[name], Transplant Immunologist,
Director Tissue Typing Laboratory,
Jewish Hospital

I. PURPOSE:

The aim of this clinical trial is to test the safety of transplanting human fetal neural retinal tissue and retinal pigment epithelium into the eyes of human patients with age-related macular degeneration. Vision in the eye to be operated on will be the poorer vision of both eyes and must be 20/200 or worse. "Retinal tissue", the layers in the back of the eye, consists of neural retina and retinal pigment epithelium. "Neural retina" is the nerve cell layer that processes light into vision. The "photoreceptor cells" in the neural retina detect the light and transform it into electrical signals, which are then transferred to the brain by other retinal cells. "Retinal pigment epithelium" (RPE) is the layer behind the neural retina which helps both to nourish the cells of

the neural retina and also to get rid of waste products. The fetal tissues used in this study will be derived from dead fetuses in the first 9-16 weeks of pregnancy obtained from elective abortions (see XV. FETAL DONOR TISSUE).

Fetal retinal transplantation is highly experimental. The research will be conducted in accordance with the prohibitions regarding the use of human fetal tissue described in Public Law 103-43, section 498B. There will be no compensation for the donor. The research will be conducted in accordance with any applicable Federal, State and local laws.

First, the technical application of the implantation instrument and its safety in the transplantation will be demonstrated in patients with 20/200 vision in one eye or worse, with functional acuity in the contra lateral eye.

Secondly, the human fetal retinal tissue will be placed in the areas beneath the retina where presently the patient has atrophy of the retinal pigment epithelium and poor retinal function.

The specific goals of this study are to demonstrate that:

1. Safety of the procedure by testing with pre-operative and post-operative vision evaluation by ETDRS (Early Treatment Diabetic Retinopathy Study) and microperimetry in patients with age-related macular degeneration and a vision of 20/200 or worse in the operated eye. The level of anticipated visual acuity improvement is unknown, but none of the patients treated thus far have lost acuity in the treated eye to the extent that this can be assessed within the limits of the testing method.

2. To determine that the donor tissue transplanted into the subretinal space will not cause harm to the host eye, the health of the retina will be assessed by clinical examination, fluorescein angiography, and the fellow eye will be examined to rule out sympathetic ophthalmia. Immediately prior to the implantation, the fluid surrounding the donor tissue will be sampled and later tested for sterility, mycoplasma, and endotoxins.

3. To confirm that the donor tissue will not provoke a rejection response in the host. A rejection response will be identified by retinal leaking surrounding the graft with staining on fluorescein and the presence of inflammation in the area of the graft. Chronic rejection would be recognized on the clinical examination by scar tissue formation in the parenchyma of the transplant.

II. DESCRIPTION OF DEVICE

Sheets of human fetal neural retina with its retinal pigment epithelium will be placed beneath the retina with the implantation instrument.

Obviously, the device is the implantation instrument and the fetal donor tissue is a biological tissue and not a device. Because of fetal tissue transplantation being under FDA supervision, the device and fetal donor tissue will be considered under the same IND number, even though the tissue is not per se a device.

III. INTRODUCTION:

The long-term goal of this proposal is to show that retinal transplantation can help to prevent blindness and to restore eyesight.

"Fetal retinal cell transplantation" includes transplantation of fetal neural retina (that will develop photoreceptors) and/or fetal retinal pigment epithelium (RPE) cells. "Retinal pigment

cell transplantation" means only transplantation of RPE cells. RPE can be "cografted" with the neuronal retina. This means that the donor RPE and the retina are not separated.

A considerable part of the American population is afflicted with incurable retinal diseases (such as macular degeneration (ARMD)^{3,65}. In this disease, blindness is due to specific degeneration of photoreceptors and/or RPE even though the neural retina that connects to the brain can still remain relatively intact^{31,41}. If the diseased photoreceptors and/or RPE can be replaced and the new cells can connect to the functional part of the host retina, a degenerated retina might be repaired and eyesight restored. There is now clear evidence that transplanted fetal neurosensory retina can re-establish connections with the residual neural network⁵³. Synapses between the transplant and host have been demonstrated, but the physiological function of these synapses is unknown⁵¹. Several publications indicate that the transplant takes part in the beneficial effects on vision^{46,57,62}. In addition, the transplanted tissue might exert a positive rescue effect on the recipient's retina, as has been shown in animal experiments *in vitro* and *in vivo*⁴³.

Advantages of fetal donor tissue

There are many reasons why we have chosen to use fetal donor cells - and not adult donor cells - for this study. The fetal cells have a high capacity to sprout processes, and to produce trophic substances that will aid host and transplant cells to establish contacts. Fetal cells can multiply, so that the transplant can grow to cover a larger area. Fetal transplants of retinal aggregates in nude rats can grow larger the younger the donor age⁴. Fetal cells can overcome the trauma of transplantation much easier than adult cells because fetal retinal cells do not depend as heavily on oxygen as adult cells⁶¹. Fetal retinal tissue is likely less immunogenic than adult tissue because it contains less microglia than older tissue^{11,44}.

Retinal transplant immunology

The subretinal space is regarded as an immunological privileged site⁵⁶ so that there is a reduced probability of rejection of allografts of fetal tissue. The neural retina is non-immunogenic but the RPE and the microglial cells in the donor retina are immunogenic^{39,63}. In spite of the potential for rejection based on the microglia in the donor retina, our hypothesis is that rejection will probably not happen because of the immunological privileged site of the subretinal space. So far, our hypothesis has been confirmed in our results with patients^{46,47}.

Most of the microglial cells are associated with blood vessels and migrate postnatally into the rat retina¹¹ and from 16 weeks gestation into the human retina⁴⁴. The number of immunogenic microglial cells in fetal rat retina is much lower than in postnatal retina¹¹. Therefore, it is likely that fetal retina is less immunogenic than postnatal retina because fetal retina still lacks inner retinal vessels. However, nobody has tested it. In our model, we have seen stable transplants in rats 6 to 10 months after surgery. This indicates that allogeneic retinal sheet transplants can be tolerated in the subretinal space of rats with retinal degeneration.

Summary of Prior Investigations

Retinal transplantation studies have involved either RPE cells (review: ^{37,38}) or cells of the neural retina (review: ^{5,7}).

Transplantation of RPE cells is aimed at delaying retinal degeneration. Several groups have shown that transplantation of healthy RPE cells can rescue photoreceptors – that would

otherwise degenerate – in an animal model of RPE dystrophy^{27,35,36}. The rescue effect is related to the age of the donor cells: only young RPE cells support long-term survival^{54,55}.

Relatively few research groups have investigated transplantation of neural retinal cells (including photoreceptors) to the retina (review: ⁷).

Our group has focused on transplantation of intact sheets of fetal retina, in contrast to disrupted or dissociated retinal cells. Such transplants can develop layers as in a normal retina with photoreceptor outer segments in contact with the host pigment epithelium⁵¹. The transplant photoreceptors express several proteins that are important for the phototransduction process that transform light into electrical signals. Some of these phototransduction proteins migrate in the photoreceptors depending on whether it is light or dark. This also occurs in transplant photoreceptors indicating that they can function normally⁵². In RCS rats and transgenic rats with retinal degeneration, sheet transplants can restore light sensitivity in an area of the superior colliculus that topographically corresponds to the placement of the transplant in the retina^{49,58,64}. Transplants can also delay the deterioration of visual acuity in retinal degenerate rats as shown by optokinetic testing⁵⁷.

We have also introduced the immunodeficient athymic rat for interspecies retinal transplantation, in which human retinal transplants are not rejected^{4,6}. Human fetal retinal transplants in rats develop all cell types according to the normal human developmental time table.^{4,9,50} We are the only team that has systemically studied long-term transplants derived from human fetal retinas as a model of retinal development⁶. Retinal tissues from human embryos of 8-16 weeks gestational age have been routinely dissected and used for transplantation to nude rats^{4,6,9,50}.

In most retinal diseases, the patients need both photoreceptors and RPE. Therefore, we have developed a procedure to transplant both tissues together⁶ which can develop to morphologically resemble a normal retina^{6,8}. Such transplants have the potential to benefit retinal diseases with dysfunctional RPE and photoreceptors such as in age-related macular degeneration.

Fetal tissue transplanted in humans

A) Fetal neural tissue transplanted to the brain

This field of research has evolved so rapidly in the last years that it is impossible to give an approximate number of subjects involved. Human fetal tissue transplantation has been aimed at a wide range of disorders, e.g., diabetes (fetal pancreas transplants), hematopoietic disorders (fetal liver or thymus transplants), and neurological disorders (especially Parkinson's disease). In clinical trials with Parkinson patients, fetal dopaminergic transplants have been able to reduce the symptoms of this incurable disease (reviews: ^{21,48}).

B) Fetal tissue transplanted to the eye

Multiple authors have reported RPE-only transplants in humans with varying degrees of rejection (see below), but at this time, this issue is not resolved. It is very likely that donor and recipients are not matched in Class I and Class II major histocompatibility complex (MHC) antigens. In our clinical trials with cografts of fetal RPE sheets together with neural retina, no rejection has been observed. The donor tissue and the recipients are tissue typed for Class I and Class II MHCs. Recipient blood is tested for antibodies to the MHC antigens to test whether an immune response occurs.

The success of RPE transplants in RCS rats (see previous section “Summary of Prior Investigations”) has led to clinical trials in ARMD patients by a team in Sweden in collaboration with Columbia University, NY ² and in the U.S. ⁶². The results were mixed, rejection was observed depending on the status of retinal degeneration, the presence of an intact blood brain barrier, and immunosuppression ²⁰. RPE transplants have been done in two patients with RP. These patients experienced improved performance on visual field testing ³⁰.

To overcome the rejection problems with allogeneic RPE, different groups have performed autologous transplants of adult RPE cells ¹⁵ and iris pigment epithelial (IPE) cells ^{1,59}, mostly to patients with “wet” age-related macular degeneration (ARMD). Improvements in visual acuity (subjective) were reported.

“Dry macular degeneration”: This form of macular degeneration consists of slow deterioration of the retina. Deposits form under the retinal pigment epithelium (RPE) called “drusen”. Drusen may block nutrition from reaching the retina from a highly vascular layer under the retina called the “choriocapillaris”. The choriocapillaris is a capillary network outside RPE that nourishes the outer layers of the retina while the inner retinal layers are supplied by retinal blood vessels coming from the optic disc. Over time, the RPE and the outer retina atrophy, or degenerate, over these areas of drusen, and a spotty loss of vision occurs. If more and more of these atrophic areas form and merge together, the macula can take on a moth-eaten appearance, with progressive loss of vision²³. This usually occurs over a period of many years. Since macular degeneration affects the RPE cells which form the outer blood-retinal barrier, degeneration of RPE can lead to loss of the immune privilege of the subretinal space.

A subgroup of dry macular degeneration, central areolar choroidal and retinal pigment epithelial dystrophy, is a hereditary macular disease characterized by bilateral, symmetric, and well-circumscribed, solitary area in the macula with choroidal and retinal pigment epithelial atrophy¹⁷. There is a bilateral, usually symmetric, bull's-eye pattern of macular dystrophy with a sharp border of underlying large or middle choroidal vessels which are usually unassociated with any surrounding lesions. Fluorescein angiography reveals a transmission window defect due to retinal pigment epithelial atrophy with remaining choriocapillaris intermingled with a hypofluorescent area of choriocapillaris atrophy. Loss of visual acuity is caused by progressive atrophy of both the retinal pigment epithelium and choriocapillaris¹⁷. There also appears to be an ARG-142-TRP mutation in the peripherin-RDS gene²⁴. The earliest degeneration here appears to affect the photoreceptors first and then later RPE and choriocapillaris.

VI. THERAPEUTIC APPROACHES TO MACULAR DEGENERATION:

Dry age-related macular degeneration therapies have dealt with vitamin and antioxidant treatments. The National Eye Institute has sponsored the AREDS (The Age Related Eye Disease Study) to test the effect of antioxidants and zinc on the progression of age-related macular degeneration¹⁰. Experimental work on membrane differential filtration is available in Europe and test centers in the U.S.

Our approach will focus on dry age-related macular degeneration. Replacement of degenerating cells by retinal pigment epithelium together with neural retina may offer success in restoring the atrophying neural retina, the pigment epithelium and part of the choroid.

VII. HYPOTHESIS TO BE TESTED:

1. Retinal transplantation by co-grafting sheets of human fetal neural retina with RPE is a safe procedure and will not have any adverse effect on the host eyes when transplanted into the subretinal space.

2. The intact sheet of transplanted human fetal neural retina with its RPE will not provoke a rejection response in the host.

VIII. DESIGN OF THE STUDY:

The participating surgeon will be [name]. The participating persons obtaining fetal retinal and RPE tissues will be [name] and [name]. [name] and [name] will participate as consultants during this project for immunology and electrophysiology testing respectively.

Before surgery, the recipient has to sign a statement that he/she is aware about the source of the donor tissue (see Research Subject Information and Consent Form), and a consent form (see Research Subject Information and Consent Form) in which the study is explained.

Ten patients with ARMD and a vision of 20/200 or worse in one eye will be selected for the study and will undergo an operation to implant fetal neural retina with RPE under the retina. Two complete examinations will be performed at least 30 days apart to confirm the visual acuity, and only one eye will be subject to surgery.

The donor tissue is taken up in a custom-made instrument with a flat, curved nozzle so that the tissue will be maintained in the correct orientation and polarity in the subretinal space of the patient's eye. (U.S. patents # 5,941,250: "Retinal tissue implantation method"; # 6,159,218: "Retinal tissue implantation tool"; # 6,156,042: "Retinal tissue implantation instrument")

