1. The donor tissue does not provoke a rejection response in the host or cause an infection. A rejection response will be identified by leaking at the site of the graft with staining on the fluorescein and presence of inflammation in the area of the graft. The presence of inflammation is defined as seeing white edematous retina with fluid over the area of the transplant. This clinical picture would coincide with the hyperfluorescent areas seen as leakage on fluorescein. Scar tissue formation in the parenchyma of the transplant is defined as seeing fibrotic tissue in the retinal pigment epithelium and neurosensory retina in the area of the transplant.

Chronic rejection will be recognized in the clinical examination by scar tissue formation in the parenchyma of the transplant.

2. To determine that the implantation procedure will not have an adverse effect on the host eye. This is obtained by assessing the health of the retina by clinical examination, fluorescein angiography, and to rule out sympathetic ophthalmia in the fellow eye. Immediately prior to implantation, samples of the fluid surrounding the donor tissue will be taken and tested later for sterility, mycoplasma, and endotoxins.

IX. METHODS USED TO IDENTIFY, RECRUIT, AND SELECT SUBJECTS:

Sample size will be ten patients per year with Age Related Macular Degeneration (ARMD). Recruitment of subjects to undergo transplantation will be from the clinical vitreoretinal practice of [name]. Randomization is not an issue in this study as only patients who meet the criteria for macular degeneration loss of vision will be used.

Criteria for selection of patients:

Inclusion Criteria:

- The subject must have decreased central visual acuity of 20/200 or worse in one eye by ETDRS vision testing for a duration of at least one year in the operated eye and have the diagnosis of age related macular degeneration; vision in the nonoperated eye must be better than the operated eye. Vision in the operated eye cannot be better than 20/200.
- Subject is older than 55 years of age
- Patient is willing to return for follow-up visits
- Patient has signed informed consent for retinal transplantation
- Patient has undergone microperimetry and Goldmann visual field testing.

Exclusion Criteria:

- Patient having a central visual acuity of better than 20/200 in one eye by ETDRS or vision worse than 20/200 in one eye by ETDRS for a duration of less than one year
- Unwilling to sign an informed consent

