- Patient under 55 years of age
- Patient having medical problems that are contraindicatory for short-term anesthesia

- Patient unwilling to return for follow-up visits
- The patient has been determined to be pregnant by patient history or by pregnancy testing in women of childbearing potential
- Features of any condition other than age-related macular degeneration in the study eye (such as pathologic myopia or presumed ocular histoplasmosis) associated with choroidal neovascularization
- Any significant ocular disease (other than choroidal neovascularization) that has compromised or could compromise vision in the study eye and confound analysis of the primary outcome.
- Inability to obtain photographs to document choroidal neovascularization, including difficulty with venous access
- History of choroidal neovascularization in the study eye
- Participating in another ophthalmic clinical trial or use of any other investigational new drugs within 12 weeks before the start of study treatment
- Prior photodynamic therapy or Macugen therapy for choroidal neovascularization
- Patient who has a history of uveitis, Coat's disease, diabetic retinopathy, glaucoma, or a cataract that prevents visualization of the posterior pole

X. POTENTIAL RISKS:

This research procedure might have unwanted side effects for different reasons.

The known and potential risks for this trial involve standard anesthesia hazards, general and/or local. The surgery would occur under retrobulbar and/or general anesthesia. Surgical complications could result in blindness and/or loss of the eye.

Adverse effects related to the "experimental pilot trial" surgery are: (1) retinal detachment, (2) vitreous hemorrhage, (3) subretinal hemorrhage and/or subretinal proliferative tissue, (4) endophthalmitis, (5) neovascular glaucoma, (6) corneal epithelial defects, (7) cataracts, (8) diplopia, (9) ptosis, (10) prephthisis or phthisis, or (11) possible complications from anesthesia, allergic reaction or side effects from certain medicines.

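### Success is framed as proof of no adverse effect, rejection or infection, with no tolerated count or severity, and zero events in about ten eyes cannot show that.

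*Protocol*

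**What the plan says.** Section VII sets two hypotheses. The first is that co-grafting "is a safe procedure and will not have any adverse effect on the host eyes when transplanted into the subretinal space". The second is that the graft "will not provoke a rejection response in the host". Goal 3 in Section I repeats the second as an aim: "To confirm that the donor tissue will not provoke a rejection response in the host". The goals as a group are introduced as things the study will demonstrate.

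Section VIII turns these into criteria for success. Criterion 1 is that the donor tissue causes neither rejection nor infection. Criterion 2 reads "To determine that the implantation procedure will not have an adverse effect on the host eye", and the sentence after it says how this is judged: clinical examination of the retina, fluorescein angiography, and exclusion of sympathetic ophthalmia in the fellow eye. No criterion states a tolerated number, proportion or severity.

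Section X lists eleven adverse effects related to the surgery. Ten are ocular, among them "4) endophthalmitis, (5) neovascular glaucoma, (6) corneal epithelial defects, (7) cataracts, (8) diplopia, (9) ptosis"; the eleventh covers anaesthesia, allergy and side effects of medicines. Section X also says that no immunosuppression will be used and that rejection is therefore a potential risk.

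On size, Section VIII says "Ten patients with ARMD and a vision of 20/200 or worse in one eye will be selected for the study" and that "only one eye will be subject to surgery". Section IX says "Sample size will be ten patients per year with Age Related Macular Degeneration (ARMD"), without giving a number of years.

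**The concern.** A safety claim stated as an absolute goes wrong in both directions. If any adverse effect counts, a minor complication that the protocol itself foresees would contradict hypothesis 1. If only some count, the protocol does not say which, and the choice would be made after the events are known. If no event occurs, the wording allows the series to be read as having confirmed safety and absence of rejection, although so few eyes leave high rates of either open.

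These criteria are the protocol's only stated rule for its conclusion. The procedure is irreversible, and Section X names blindness and loss of the eye among its possible consequences, so an overstated conclusion would matter to later patients.

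**Working it through.** **Inputs.** Ten patients with one operated eye each (Section VIII). Ten ocular complications listed, without rates (Section X). No rate given for rejection. The one event rate quoted is sympathetic ophthalmia after repeated vitreoretinal surgery, 1/800 = 0.125% (Section X). The sample size comes with no error rate, event rate or margin, so there is no planned calculation to reproduce.

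**Step 1: which events count.** Set side by side, the passages differ.

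- Hypothesis 1: any adverse effect on the host eye.
- Criterion 2: an adverse effect as judged by retinal examination, angiography and the state of the fellow eye.
- Section X: ten ocular events, some retinal (detachment, subretinal haemorrhage) and some not (corneal epithelial defect, ptosis).

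A corneal epithelial defect contradicts hypothesis 1 but would not clearly fail criterion 2.

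**Step 2: chance of an event-free series.** With per-eye probability p of a counted event and independent eyes, P(0 of 10) = (1 − p)^10. The values of p are assumptions, because the protocol gives none.

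| Assumed p per eye | P(0 of 10) |
|---|---|
| 1% | 0.99^10 = 90.4% |
| 5% | 0.95^10 = 59.9% |
| 10% | 0.90^10 = 34.9% |
| 20% | 0.80^10 = 10.7% |

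The break-even rate solves (1 − p)^10 = 0.5, so p = 1 − 0.5^(1/10) = 6.7%. Above it, at least one event is more likely than not. If the ten ocular complications were independent and equally frequent (a further assumption), 1 − (1 − 0.067)^(1/10) ≈ 0.7% each would reach it.

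**Step 3: what zero events would show.** This step needs no assumed rate. The exact upper 95% limit for 0 of n is 1 − 0.05^(1/n) one-sided and 1 − 0.025^(1/n) two-sided. Section IX leaves the final n open, so n = 20 and n = 30 (two or three years at ten per year) are shown as well.

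| n | One-sided | Two-sided |
|---|---|---|
| 10 | 25.9% | 30.8% |
| 20 | 13.9% | 16.8% |
| 30 | 9.5% | 11.6% |

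The 10% row of step 2, read for rejection, gives the converse: a true 10% rejection rate would produce no rejection in ten patients in 34.9% of such trials.

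**Step 4: sympathetic ophthalmia.** At the quoted 0.125%, P(no case in 10) = 0.99875^10 = 98.8%. Seeing none is almost certain and says next to nothing about the risk.

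**The case against.** Several stronger readings are tempting, and the documents do not support them.

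- *One corneal abrasion fails the trial.* This follows from the wording of hypothesis 1 only. Criterion 2 is judged on the retina and the fellow eye, so under the success criteria it is at best unclear.
- *The protocol expects these complications.* It calls them known and potential risks, and one of the eleven is not ocular.
- *The rule is unlikely to be met.* The documents give no complication rate. At 1% or 5% per eye, an event-free series is the likelier outcome. For rejection, Section III reports none in the group's earlier co-graft trials.
- *There is an explicit rule that no eye may have an event.* No sentence says so, and criterion 2 is phrased as an aim. But with no tolerated count or severity anywhere, the text offers no other threshold.

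It can also be said that a first safety study need not be powered, that no series of this size could detect a 0.125% risk, that the protocol itself calls the work highly experimental, and that intervals and tabulations are commonly left to a statistical analysis plan. All of that is fair. Ten patients is not the defect, and the absence of an interval formula is not either. What stands is that the protocol itself fixes the conclusion as absence of harm, which the design cannot deliver. An analysis plan could add intervals, but it would still be working under hypotheses and success criteria worded that way.

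**Conclusion.** The concern holds as a fault in the stated conclusion rule. The absolute wording conflicts with Section X, leaves open which events count, and would let a small uncontrolled series be reported as confirming what it cannot confirm.

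The firm part rests only on the number of patients. At n = 10, an event-free series is compatible with a true rate of about one eye in four (25.9% one-sided) or higher (30.8% two-sided). If recruitment ran to 20 or 30 patients the limits would be lower but still far from absence.

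The conditional part is the chance of meeting the rule, which turns on whether the unknown per-eye rate of counted events lies above or below 6.7%. A reader might infer that the trial is bound to fail its own criteria. The documents do not establish that, least of all for rejection.

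**What to change.** 1. Align hypothesis 1 with criterion 2, so that one statement says which events count.
2. Restate both, together with the rejection and infection criteria, as estimation. Report the count and exact 95% interval for rejection, for infection, and for a set of sight-threatening events from the Section X list that the investigators name in advance. Endophthalmitis could fall under infection or under that set, so say where it is counted. Tabulate the remaining surgical events separately.
3. In Sections I, VII and VIII, replace *confirm* and *demonstrate* with *estimate*.
4. Reconcile the ten patients of Section VIII with the ten per year of Section IX, and state the two-sided upper limit that zero events would leave at the final number: 30.8% for 10, 16.8% for 20, 11.6% for 30.

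The change adds no patients, visits or tests. The cost is editing in Sections I, VII, VIII and IX, and a stated conclusion less favourable than the present wording allows.
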